### 3.4.3 POST PROCEDURE

Categorical variables will be summarized (number and percentage):

- Subject Success (whether all planned implants were successfully delivered on first attempt)
- Number of Implants Delivered
- Any Adverse Events Prior to Discharge

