#### ANALYSIS SETS 2.2.

Unless otherwise specified, all analyses will use the modified intent-to-treat analysis set (mITT), which is defined below.

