# 2.2.1. ANALYSIS SETS FOR EFFICACY AND SAFETY

The ITT analysis set will primarily be used for safety evaluations and will include all subjects who begin the implant procedure. Subjects who are consented but do not begin the implant procedure will not be included in the ITT analysis set. Because this is a singlearm, open-label study, the exclusion of subjects who do not begin the implant procedure is unlikely to result in biased response estimates. Subjects who begin the implant procedure but do not successfully receive an implant will be included in the ITT analysis set.

The mITT analysis set will consist of all subjects who successfully receive at least 1 Spirox LateraTM implant. Analyses supporting the primary and major secondary endpoints will, to the extent possible, be based on the mITT analysis set. Safety evaluations for events within 7 days of the implant procedure will be based on the ITT analysis set, and cumulative adverse events at 6 months will be based on the mITT analysis set. An important subgroup of the mITT analysis set is the 6 Month Evaluable (6ME) Set, which includes subjects with 6 month post-implant NOSE score assessments in clinic or by telephone.

The per-protocol (PP) analysis set will consist of all mITT subjects who have no major protocol deviations or events that might impact NOSE scores. These deviations may include changes to background nasal medications, prohibited medications and additional procedures prohibited by the protocol.

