# 3.4 LATERATM IMPLANT

### 3.4.1 PROCEDURE INFORMATION

Procedure information will be summarized for the ITT Analysis Set by whether the subject underwent a unilateral or bilateral implant placement for subject-level variables. Continuous variables including anesthesia duration, procedure duration and LateraTM implant duration will be summarized with descriptive statistics (N, mean, SD, median, and range). Categorical variables summarized by number and percentage include:

- Procedure Type: LateraTM Alone, LateraTM + Septo, LateraTM + Turbs, LateraTM + Septo + Turbs
- Turbinate Reduction Method
- Any Adverse Events During Procedure

Device delivery data will be summarized by nostril. For descriptive tables, the within-subject correlation will be ignored. The following categorical variables will be summarized (number and percentage):

- Implant Successfully Loaded into Delivery Tool
- Implant Successfully Delivered
- Implant Exposed
- Implant Retrieved
- Delivery Device Malfunction
- LateraTM Implant Malfunction

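### SAP 3.4.3 names no analysis set, so the default puts Subject Success and its two companion items in mITT, which leaves out any subject in whom no implant was delivered

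*SAP*

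**What the plan says.** SAP 3.4.3 introduces its list only with "Categorical variables will be summarized (number and percentage" and gives three items: "Subject Success (whether all planned implants were successfully delivered on first attempt", Number of Implants Delivered, and Any Adverse Events Prior to Discharge. It states no denominator.

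SAP 2.2 supplies one: "Unless otherwise specified, all analyses will use the modified intent-to-treat analysis set (mITT), which is defined below". SAP 2.2.1 then sets the entry condition: "The mITT analysis set will consist of all subjects who successfully receive at least 1" implant. The same section says where the others go: "Subjects who begin the implant procedure but do not successfully receive an implant will be included in the ITT analysis set". Protocol 10.3 defines ITT and mITT in the same way.

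The neighbouring section, SAP 3.4.1, does name a set: "Procedure information will be summarized for the ITT Analysis Set by whether the subject underwent a unilateral or bilateral implant placement". It also contains a by-nostril delivery table. SAP 3.3 lists both the ITT and the mITT sets in the disposition summary.

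For early adverse events, SAP 2.2.1 and 5.1 assign the first 7 days after the procedure to ITT.

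**The concern.** Subject Success is the SAP's subject-level measure of whether the device could be delivered as planned. The worst result on that measure is that no implant is delivered. Under the default rule, that result removes the subject from the set on which the measure is reported, so entry to the denominator depends partly on the outcome being counted. The resulting percentage can only equal or exceed the rate among everyone in whom delivery was attempted.

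The same default reaches the other two items. Number of Implants Delivered could never be zero. Adverse events before discharge would omit subjects whose procedure was begun but ended without an implant, although the SAP's own safety rule places events this early in ITT.

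What is at stake is one descriptive percentage. It still deserves a correct denominator, because Protocol Appendix II says the data may be used for regulatory applications and publications, where a delivery success rate could be quoted on its own.

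**Working it through.** The documents give no delivery success figure and no delivery failure rate, so there is no stated number to reproduce. The first step is textual; the second shows the size under assumed counts.

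**Step 1: which set applies**

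- SAP 3.4.3: no set named.
- SAP 2.2: where no set is named, mITT.
- SAP 2.2.1: mITT requires at least one successful implant; a subject who began and received none is in ITT only.
- Result: for Subject Success, a subject with no implant is neither a success nor a failure. The subject is not counted.

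**Step 2: size**

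Inputs:

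- N, subjects who begin the procedure (ITT). Assumed to be 170, the enrolment ceiling in the SAP sample size section. Some enrolled subjects may not begin, so the true N could be smaller.
- f, subjects who receive no implant. Assumed, range 0 to 10.
- q, subjects with at least one implant who still fail the definition (one side failed, or a second attempt was needed). Assumed to be 10; q = 5 and q = 0 are shown for comparison.

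Formulas:

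- Successes: S = N − f − q
- ITT rate = S / N
- mITT rate = S / (N − f)
- Ratio, mITT to ITT = N / (N − f)

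Results for N = 170, q = 10 (differences taken before rounding):

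| f | S | ITT rate | mITT rate | Difference, points |
|---|---|---|---|---|
| 0 | 160 | 160/170 = 94.1% | 160/170 = 94.1% | 0 |
| 1 | 159 | 159/170 = 93.5% | 159/169 = 94.1% | 0.6 |
| 2 | 158 | 158/170 = 92.9% | 158/168 = 94.0% | 1.1 |
| 5 | 155 | 155/170 = 91.2% | 155/165 = 93.9% | 2.8 |
| 10 | 150 | 150/170 = 88.2% | 150/160 = 93.8% | 5.5 |

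The ratio is 170/168 = 1.012 at f = 2 and 170/165 = 1.030 at f = 5.

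The choice of q hardly changes the gap. With q = 5 the rates are 163/170 = 95.9% against 163/168 = 97.0% at f = 2, and 160/170 = 94.1% against 160/165 = 97.0% at f = 5. With q = 0 the mITT rate is 100% whatever f is, while the ITT rate is 165/170 = 97.1% at f = 5.

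The two middle columns of the table show the practical defect. As complete failures rise from 0 to 10, the ITT rate falls from 94.1% to 88.2%, while the mITT rate moves only from 94.1% to 93.8%. The mITT rate barely responds to the failures that matter most.

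**Step 3: the other two items**

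- Number of Implants Delivered: membership of mITT means at least one, so a zero row is empty by definition.
- Any Adverse Events Prior to Discharge: SAP 3.4.1 tabulates adverse events during the procedure in ITT, and SAP 2.2.1 and 5.1 put the first 7 days in ITT. Protocol 10.4.4 uses a longer acute window, through 1 month, but also in ITT. The default in 3.4.3 would put the events between these two tables on a narrower set.

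**The case against.** The strongest reply is that ITT was intended. Section 3.4.3 sits under the same 3.4 heading as 3.4.1, which assigns its subject-level procedure variables to ITT, and the items in 3.4.3 are subject-level procedure variables too. The by-nostril table in 3.4.1 also relies on that one opening statement. The numbering jumps from 3.4.1 to 3.4.3, so it is hard to tell how far the statement was meant to reach. For pre-discharge adverse events, the 7-day rule can itself be read as specifying ITT. All this is plausible as to intent. It does not settle the text: 3.4.3 is a separate numbered section, nothing extends ITT to it, and SAP 2.2 says what applies when a section is silent. A programmer following the SAP literally would use mITT. If ITT was meant, saying so costs nothing.

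Some stronger inferences should be resisted.

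- *The rate is fixed near 100% by construction.* It is not. Bilateral subjects with one failed side, and subjects who needed a second attempt, stay in mITT and count as failures.
- *The rate is 100% in planned unilateral cases.* SAP 3.4.3 plans no split by laterality. If it borrowed the split from 3.4.1, it would borrow ITT with it, and the problem would disappear.
- *Complete failures are concealed.* They are not. Disposition lists the ITT and mITT sets, so f is the difference between their counts, and delivery by nostril is tabulated in 3.4.1.
- *SAP 3.4.1 also drops these subjects, because they fit neither the unilateral nor the bilateral column.* The wording about the placement a subject underwent may cover an attempted placement. That is an ambiguity, not an error.

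**Conclusion.** The point holds on the SAP as written. The stated default gives the wrong denominator for Subject Success, rules out a zero category for Number of Implants Delivered, and separates pre-discharge adverse events from the set used for other early events.

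The size is conditional. The rate is overstated by the factor N/(N−f): with an assumed 170 subjects and 10 other first-attempt failures, by 1.1 points at f = 2 and 2.8 points at f = 5. It is not overstated at all if every subject who begins the procedure receives at least one implant. The documents do not say how often complete failure occurs, so these counts are illustrations, not predictions.

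This is a minor point. Delivery success is not a primary, secondary or exploratory endpoint and carries no hypothesis. A reader might infer that the efficacy result or the type I error is affected; neither is, because the primary analysis has its own stated set, subjects with a 6-month NOSE score. Being able to recover f elsewhere limits the harm, but it does not correct the percentage as it would be printed.

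**What to change.** In SAP 3.4.3, state that all three items are summarized for the ITT set, with every subject who began the procedure in the denominator, and list zero as a category of Number of Implants Delivered. Subjects with no implant then count as failures for Subject Success.

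Optionally, in SAP 3.4.1, say that the unilateral/bilateral split is by planned placement, so that every ITT subject has a column.

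The cost is SAP wording only. No new data, sample size change or change to the primary analysis follows. The reported success rate may be slightly less favourable if complete failures occur.

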#### **DURATION OF FOLLOW-UP** 3.5.

Follow-up duration is defined as the number of days from implant until the first of early study discontinuation, completion of the 24 months of follow-up visit, study termination, or database lock. The cumulative distribution of time under follow-up will be calculated and summarized using Kaplan Meier methods.

For time-dependent safety analyses of adverse events, the duration of follow-up will be defined as the number of days from implant until the last date when the presence or absence of the event in question could be assessed. For example, for Adverse Events (AE), the duration of follow-up would be the number of days from implant to the onset of the first AE for subjects reporting any event, and the number of days between implant and the last date when AEs were assessed for those who did not experience any event.

#### PROTOCOL DEVIATIONS 3.6.

The following list of protocol deviations may affect the interpretation of the primary and major secondary efficacy endpoints, and therefore, subjects with any of these protocol deviations will be excluded from the PP analysis set. The complete list of subjects with these protocol deviations will be identified prior to database lock, and a summary of reasons for exclusion will be tabulated.

- Subject did not meet eligibility criteria
- Follow-up evaluation performed outside protocol-required window
- Other protocol deviation that may affect the interpretation of efficacy endpoints, with justification

#### **EFFICACY** 4.

The efficacy analyses will be performed based on the mITT analysis set. The analyses will be repeated for the PP set to determine the impact of protocol deviations on the primary results.

#### ANALYSIS SPECIFICATIONS 4.1.

### 4.1.1. LEVEL OF SIGNIFICANCE

Unless otherwise specified, all statistical tests will be interpreted at a 2-sided significance level of 5% and all confidence intervals at a 2-sided confidence level of 95%. The study type 1 error rate of 5% will all be allocated to the primary endpoint hypothesis, so p-values beyond the primary hypothesis should be considered descriptive.

### 4.1.2. DATA HANDLING RULES

#### PRIMARY EFFICACY ENDPOINT 4.2.

### 4.2.1. DEFINITION

The primary endpoint will be the proportion of treatment responders at 6 months post procedure. Subjects will be classified as responders if they meet at least 1 of the following criteria:

- The 6 month NOSE score category has improved from the baseline category by 1. at least 1 level
- The 6 month change from the pre-implant average NOSE score is  $\geq 20\%$ 2.

Subjects will be classified as non-responders if neither of these criteria is met. The baseline category is defined based on the pre-study average within-subject NOSE score.

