7.2. STUDY EVALUATIONS METHODS

7.2.1. Nasal Obstruction Symptom Evaluation (NOSE) Scale

The Nasal Obstruction Symptom Evaluation (NOSE) Scale¹⁸ is a Patient-Reported Outcome (PRO) instrument that will be administered to capture subject perception of the degree of nasal airway patency. The NOSE scale will be completed at the Screening, Baseline, 1 Month, 3 Month, 6 Month, 12 Month, 18 Month and 24 Month visits. The NOSE scale may additionally be completed at the Treatment Visit if more than 1 month from Screening Visit.

The NOSE scale is a validated instrument, which was developed by the American Academy of Otolaryngology—Head and Neck Surgery (AAO-HNS), and has been used in several clinical trials. The scale is brief, easy to complete, and is an important tool for pre- and post-intervention evaluation of symptoms in subjects with nasal obstruction. NOSE Scale allows subjects to quantify their symptoms based on the severity of obstruction.

Subjects will be asked, "Since your last follow up visit, how much of a problem were the following conditions for you?" Specifically, subjects will be asked to rate their perceptions on the Likert scale with respect to the following characteristics:

- Nasal congestion or stuffiness
- Nasal blockage or obstruction
- Trouble breathing through my nose
- Trouble sleeping
- Unable to get enough air through my nose during exercise or exertion

Participants will rate their responses using a Likert scale with response options 0, 1, 2, 3 or 4, as follows:

- (0) Not a Problem
- (1) Very Mild Problem
- (2) Moderate problem
- (3) Fairly Bad Problem
- (4) Severe problem

The responses are rated along the continuum, with a rating of "0 – not a problem" indicating no problem breathing, with a completely free flow of air through the nasal airway; "1 – very mild problem", with only slight obstruction in airflow; "2 – moderate problem", with mouth breathing considered easier; "3 – fairly

Spirox Latera™ implant support of lateral wall cartilage (LATERAL-OR) study	Version 2.0
SPI-CP-301	September 7, 2017

bad problem," with considerable obstruction to airflow; and a rating of "4 – severe problem," with complete blockage and obstruction of the nasal passageway, where the subject cannot breathe through the nose and can only mouth breathe. A copy of the Nasal Obstruction Symptom Evaluation Scale questionnaire is attached (See Addendum B).

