10.4. DESCRIPTION OF STATISTICAL METHODS

10.4.1. GENERAL APPROACH

This is a prospective, single arm, open label controlled study to evaluate the impact of Spirox Latera[™] alone or in conjunction with other procedures over 24 months of follow-up. Each patient will serve as his or her own control.

The study reference day (Day 1) is the day of the Implant procedure.

"Baseline" NOSE score refers to the measurement taken prior to the start of the procedure during the baseline visit.

Continuous variables will be summarized with descriptive statistics (N, mean, SD, median, quartiles), and categorical variables will be summarized as N (%).

Unless otherwise indicated, all p-values and confidence intervals will be 2-sided.

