10.4.2. ANALYSIS OF THE PRIMARY EFFICACY ENDPOINT(S)

The primary endpoint will be the proportion of treatment responders at 6 months post procedure.

Responder is defined as subject that has at least one (1) NOSE class improvement or at least 20% NOSE score reduction

Subjects will be classified as non-responders if neither of these criteria is met.

NOSE score is a patient-reported outcome instrument which measures the impact of nasal obstruction on quality of life. It is scored in increments of 5 points, and the total score is calculated as the sum of all 5 questions multiplied by 5, where the range is 0 (asymptomatic) to 100 (most extreme deleterious impact on quality of life). The NOSE score classes¹⁶ are based on the total calculated score:

Mild: 5 – 25 points Moderate: 30 – 50 points Severe: 55 – 75 points Extreme: 80 – 100 points

This primary hypothesis will be evaluated for the 6 Month Evaluable Population using a -2-sided exact test²³, and the corresponding exact (Clopper-Pearson) 2-sided 95% confidence interval will be calculated. The null hypothesis that the proportion of responders is \neq 0.5 will be rejected if the p-value is < 0.05.

Sensitivity analyses will be conducted to determine the impact of missing data on these results. These analyses will depend on the extent of missing data, and will be detailed in the SAP, but may include:

- 1. Last observation carried forward (LOCF)
- 2. Subjects with missing data classified as non-responders

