#### TRIAL DESIGN 1.2.

As described in the protocol, this is a prospective, multi-center, non-randomized study of the Spirox LateraTM implant in an intraoperative setting. These devices will be used to treat nasal valve collapse in approximately 170 subjects with extreme or severe symptoms of nasal obstruction. Follow-up assessments will occur at 1, 3, 6, 12, 18, and 24 months after device implant.

The primary performance measure of the Spirox LateraTM implant will be based on the Nasal Obstruction Symptom Evaluation (NOSE) instrument. This instrument measures the burden of nasal obstructive symptoms in increments of 5 points, and the total score ranges from 0 (asymptomatic) to 100. Categories for clinical severity are:

Mild: Total score 0-25 points

Moderate: Total score 30 – 50 points

Severe: Total score 55 – 75 points

Extreme: Total score 80 – 100 points

The primary endpoint will be the proportion of device responders at the 6 month followup visit. Subjects will be classified as responders if they meet at least 1 of the following criteria:

- The 6 month NOSE score category has improved from the baseline category by 1. at least 1 level
- The 6 month change from baseline NOSE score is  $\geq 20\%$ 2.

Subjects will be classified as non-responders if neither of these criteria is met.

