### GENERAL ANALYSIS DEFINITIONS 2.

#### VISIT WINDOWS 2.1.

The reference day is study day 1, the day of device implant. Study day will be calculated relative to the date of implant.

Baseline will be defined as the pre-implant measure closest to or including Day 1 (prior to implant procedure).

If a subject has two or more actual visits in one analysis visit window, the visit closest to the target day will be used as the study visit for that analysis visit window. If two study visits are the same number of days from the target day within the same visit window, the later visit will be considered the study visit for that target day. Even though all visits will be allocated an analysis visit window, only planned protocol visits for each variable

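### The SAP's primary responder rule departs from the protocol: an undirected change replaces a reduction, and an undefined average of pre-implant scores replaces the baseline-visit NOSE score

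*SAP*

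**What the plan says.** Protocol 10.4.2 gives the rule with a direction: "Responder is defined as subject that has at least one (1) NOSE class improvement or at least 20% NOSE score reduction". Protocol 10.4.1 fixes the reference value as one score; baseline "NOSE score refers to the measurement taken prior to the start of the procedure during the baseline visit".

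The SAP gives three accounts:

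- **Section 1.2**, second criterion: "The 6 month change from baseline NOSE score is" at least 20%. There is no average and no direction.
- **Section 2.1**, for all variables: "Baseline will be defined as the pre-implant measure closest to or including Day 1 (prior to implant procedure").
- **Section 4.2.1**, for the primary endpoint: "The 6 month change from the pre-implant average NOSE score is" at least 20%, and "The baseline category is defined based on the pre-study average within-subject NOSE score". The average is called pre-implant in one line and pre-study in the other.

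The number of pre-implant scores varies by subject. NOSE is scheduled at screening and baseline, and Protocol 7.2.1 adds a possible third: "The NOSE scale may additionally be completed at the Treatment Visit if more than 1 month from Screening Visit". Under the footnotes to Protocol 7.7, the screening form is not required when Visits 1 and 2 are combined, so some subjects will have only one score.

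On the scale itself, SAP 1.2 says "This instrument measures the burden of nasal obstructive symptoms in increments of 5 points", and both documents give the classes only for such values (Moderate 30–50, Severe 55–75, Extreme 80–100).

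**The concern.** This rule decides who counts as a success on the only endpoint that carries type 1 error. It is also reused for the response proportions at the other visits. Three things are unsettled.

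1. **Direction.** Read literally, a subject who worsens from 60 to 75 (a change of 25%) meets the second SAP criterion.
2. **Reference score.** The baseline-visit score, the score closest to Day 1 and an average can all differ. The first two coincide unless NOSE is repeated on the treatment day.
3. **Class of an average.** The mean of two scores on a 5-point grid can be 52.5 or 77.5, and neither value belongs to a stated class.

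Two analysts following the two documents could report different response rates and confidence intervals. The study is open-label with one arm, so an unsettled baseline also leaves a choice open while results are visible.

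**Working it through.** **The plan's own sample size figure.** The rejection count is the smallest r with P(X ≥ r | n, 0.50) ≤ 0.025; power is P(X ≥ r | n, 0.66).

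| n | Source | r | Two-sided alpha | Power |
|---|---|---|---|---|
| 120 | SAP sample size section | 72 | 0.035 | 93.0% |
| 150 | Protocol 10.5 | 88 | 0.041 | 97.5% |

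Both meet the stated power above 90%. The responder definition does not enter these figures, so the fix leaves them unchanged.

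**Direction, by enumeration.** Baseline 55 to 100 (entry requires at least 55) and 6-month score 0 to 100, both in steps of 5, give 10 × 21 = 210 pairs.

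- With change taken as absolute, 26 pairs are worsenings of 20% or more that pass the second criterion. Every baseline from 55 to 80 has at least one.
- With change signed as 6-month minus baseline, the same 26 pass and four protocol responders are lost: 70 to 55, 75 to 55, 75 to 60 and 100 to 80.

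For frequency, Protocol 2.2 reports a 6-month percent change with mean −56.2 and SD 37.85. Taken as normal, P(change ≥ +20%) = 1 − Φ((20 + 56.2)/37.85) = 1 − Φ(2.01) = 2.2%. Simulated on the 5-point grid it is 1.4% to 3.2%, about 2 to 5 of 150.

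**Reference score, by enumeration.** Assume the average is of the screening and baseline-visit scores, both 55 to 100.

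- Of 100 score pairs, 10 average 77.5 and have no class.
- The other 90 pairs × 21 six-month scores give 1,890 combinations. Status differs from the protocol in 106: 52 become responders and 54 become non-responders. These are counts of combinations, not expected frequencies.

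| Screening | Baseline visit | 6 months | Protocol | SAP average |
|---|---|---|---|---|
| 85 | 75 | 75 | No class change, 0%: non-responder | 80, Extreme to Severe: responder |
| 80 | 70 | 60 | Down 14.3%, same class: non-responder | 75, down 20%: responder |
| 70 | 80 | 75 | Extreme to Severe: responder | 75, no change: non-responder |

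**Averages between classes.** At 77.5, a 6-month score of 65 is a fall of 12.5/77.5 = 16.1%, so the second criterion fails and status depends on whether 77.5 is called Severe or Extreme. The same holds at 70 and 75; a score of 60 (22.6%) passes anyway. At 52.5 the undecided scores are 45 and 50.

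**Size, by simulation.** The documents do not give the spread of repeated scores, so these inputs are assumptions: mean 70 to 76.7, between-subject SD 12 to 15, within-subject SD 5 to 10, independent visit noise, rounding to 5, screening at least 55. The percent change has SD 37.85 and is applied to either the baseline-visit score or the true score. All subjects are given two pre-implant scores.

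| Mean change | Response rate | Undecided | Status switches | Shift in rate |
|---|---|---|---|---|
| −56.2% | 85–87% | 0.7–0.9% | 1.6–3.9% | up to 1.4 points |
| −40% | 74–76% | 1.1–1.3% | 2.3–5.5% | up to 1.7 points |
| −28% | 63–65% | 1.3–1.6% | 2.7–6.6% | up to 1.9 points |

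The average falls between classes in 7.7% to 9.0% of subjects. The last row is close to the planned 66%; the 80% reported for the earlier trial lies between the first two rows.

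**Effect on the test.** At 66%, 0.66 × 150 = 99 responders are expected against 88 needed, a margin of 11. A shift of 1.9 points is 0.019 × 150, about 3 subjects.

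**The case against.** **The direction point is a drafting slip.** The first criterion says improved and the protocol says reduction, so no analyst is likely to score a worsening as success. This stands, and the frequency of large worsenings should not drive the severity. That frequency also depends on the assumed effect: at a mean change of −28% it rises to roughly 6–11%. The normal model is rough as well, since at −56.2% it puts about 12% of subjects below −100%, an impossible value.

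**The missing detail may be a text loss.** SAP 4.1.2 has a heading and no body, and SAP 2.1 breaks off mid-sentence. A list of averaged scores or a rounding rule could have stood in either place. This stands for both points. It does not remove the conflict between an average in SAP 4.2.1 and a single score in Protocol 10.4.1.

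**The specific section governs the general one.** SAP 4.2.1 could be read as overriding SAP 2.1 for the primary endpoint, with the average meaning all available pre-implant scores. That is a reasonable reading, but neither document states it, and SAP 1.2 defines the same endpoint without an average. Protocol 10.1 leaves further detail to the SAP; a different baseline is a substitution.

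**The switches do not fully cancel.** With half-points put in the higher class, the average raised the response rate in every scenario, and at within-subject SD 10 up to about a third of the switching was not offset. This stands, and the bound of 1.9 points already includes it.

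**Averaging is legitimate and more reliable.** This is true, so the fix leaves that option open.

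**Conclusion.** The concern holds. The primary responder rule differs between protocol and SAP, and within the SAP, in its reference score; the missing direction is a lesser wording error. The consequence is that the reported response rate and interval are not uniquely defined. The primary conclusion is not under serious threat: under the stated assumptions the rate moves by at most 1.9 points, about 3 of 150 if every subject had two pre-implant scores, against a margin of 11 responders at the planned rate. The number of subjects with more than one pre-implant score is not given, and those with one score are unaffected. The switching figures rest on assumed within-subject variability and on averaging the screening and baseline-visit scores. It should be fixed before database lock.

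**What to change.** In SAP 1.2 and 4.2.1, write the second criterion as 100 × (baseline − 6-month score)/baseline ≥ 20.

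In SAP 4.2.1, and for NOSE only in SAP 2.1, use the protocol's single baseline-visit score for both criteria. If a repeated treatment-day score is meant to replace it, say so in the same words in both documents.

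If the average is preferred, list the scores that enter it, state what happens when only one exists, give class cut-points that leave no gaps, use one term for the average, and amend Protocol 10.4.1 to match.

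The cost is a few sentences of wording and one derivation, with no new data and no change to sample size or power. The single score gives up a little reliability compared with an average.
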